#### **7.4 Withdrawal of individual subjects**

Subjects can leave the study at any time for any reason if they wish to do so without any consequences. The investigator can decide to withdraw a subject from the study for urgent medical reasons or if continuing participation is deleterious for the subject's wellbeing. For example,  $\geq 20\%$  weight loss or an allergic reaction to the food supplement or diet ingredients will be a reason for withdrawal from further participation. All data generated up to the time of discontinuation from the study will be analysed and the reason for discontinuation will be documented.

##### **7.4.1 Specific criteria for withdrawal**

Subjects meeting the following criteria must be withdrawn from the trial:

- occurrence of any AE, or abnormality in a laboratory assessment which, in the opinion of the investigator, warrants the subject's permanent withdrawal from the trial.
- urgent medical reasons or if continuing participation is deleterious for the subject's wellbeing.
- patient noncompliance, defined as refusal or inability to adhere to the trial schedule or procedures.
- at the request of the subject, investigator or regulatory authority.
- subject becomes pregnant.
- subject dies or is lost to follow-up.

#### **7.5 Replacement of individual subjects after withdrawal**

The sample size calculation for this study is given in paragraph 4.4. A 25% protocol violator and/or drop-out rate is taken into account. Therefore an inclusion of 30 subjects per study group is aimed. However, drop-outs from this study that occur during the first 2,5 months because of schedule problems, pregnancy or non-diabetic medical reasons may be replaced in order to reach 23 subjects per study group to complete the study. If a subject discontinues from the study prematurely the reason must be fully evaluated and recorded appropriately in

source documentation and the eCRF. If the subject is being withdrawn because of an AE, that AE must be indicated as the reason for withdrawal.

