#### 4. STUDY POPULATION

##### 4.1 Population (base)

The study population consists of South Asian patients with type 2 diabetes and microalbuminuria between 18-75 years old. In total 90 patients will be included in the study.

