#### **4.4 Sample size calculation**

The primary outcome will be improvement of the Microvascular Health Index after 3 months. The sample size is chosen according to a pilot study with 13 healthy volunteers receiving the food supplement Endocalyx™ for 3 consecutive months. After 3 months, a 31% improvement in Microvascular Health Index was demonstrated, expressed in a significant increase of the MHI from 1.05 at baseline, to 1.38 at 3 months (improvement of 0.33).

Group sample sizes of 23 per group achieve 80% power to detect a difference of 0.35 between the null hypothesis that group improvement means are 0.0 and the alternative hypothesis that the improvement mean of group 2 or 3 is 0.35 with estimated group standard deviations of 0.41 with a significance level (alpha) of 0.05000 using a two-sided two-sample t-test. If we anticipate a 25% drop out rate per group, we will need 30 patients per group.

Therefore, we decided to enrol a total number of 90 patients in this study.

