### 7.2 Randomisation, blinding and treatment allocation

Eligible patients will be randomized during the run in period into the FMD, food supplement or placebo arm after given informed consent. Randomisation will be performed by the LUMC pharmacy. The placebo and food supplement group will be double blinded. The pharmacy will store the randomization code. The investigator or pharmacy can deblind the subjects in the occurrence of any AE, SAE, or abnormality in a laboratory assessment which, in the opinion of the investigator, warrants the subject's permanent withdrawal from the trial.

Patient specific data will be stored under a subject identification code and randomization number for each patient. There will be a subject identification code list that links the codes to a subject. This list will be stored for 15 years by the principal investigator. Data will be presented for the complete intention-to-treat population as well as the per protocol population.

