### 10.3 Benefits and risks assessment, group relatedness

The prevalence of type 2 diabetes is high in South Asian patients [22]. These patients have a 40 times higher risk of developing ESRD and a faster progression to renal failure compared to West European patients [54]. This is may be linked to increased systemic and glomerular inflammation in these patients [24, 55, 56]. Consequently, these patients will probably have an impaired endothelial glycocalyx with high heparanase activity and would benefit the most from treatments that support the glycocalyx homeostasis and reduce inflammation burden. To date, treatments for diabetic nephropathy are insufficient in preventing the development of ESRD. The interventions in this study can be used as add-on dietary interventions to reduce residual albuminuria and progression of renal disease.

The intervention burden in the FMD arm is for 5 days a month and in the other arms by taking daily capsules. Blood and urine sampling and non-invasive SDF imaging will be done at 3 time points in all intervention groups. In addition, patients are frequently monitored due to the possible effects of the interventions on glucose levels and insulin sensitivity. For the FMD group this means frequently measuring glucose values trough a finger prick.

Patients in the diet group have a risk of the occurrence of hypoglycemia during the study. In the days of the diet, this risk is reduced by stopping the hypoglycemic drugs that can cause hypoglycemia. After the diet, patients are asked to measure their glucose levels regularly.

The dosages of the hypoglycemic drugs can be altered if needed.

Other risks of the interventions may be an allergic reaction to one of the components of the diet or the food supplement. However, if eligible patients already are known with specific food allergies, they are excluded from the study. Effects on kidney function and liver function will be monitored during the study, but are not expected as a result of the interventions. In our opinion, the risk of the interventions is reduced within our study design and therefore the limited side effects and possible beneficial effects of the interventions on metabolic parameters, microvascular health and albuminuria justify participation in this study.

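### Section 7.5 replaces selected drop-outs up to a per-arm completer target without saying how replacements are allocated, which weakens concealment for the open diet arm

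*Combined protocol and SAP*

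**What the plan says.** Section 4.4 sets the completer target: "Group sample sizes of 23 per group achieve 80% power to detect a difference of 0.35". It then allows for 25% drop-out and arrives at 30 per group, 90 in all. Section 4.1 repeats the total: "In total 90 patients will be included in the study".

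Section 7.5 restates the allowance, "A 25% protocol violator and/or drop-out rate is taken into account", and the recruitment aim, "Therefore an inclusion of 30 subjects per study group is aimed". It then adds an exception: "drop-outs from this study that occur during the first 2,5 months" and that arise "because of schedule problems, pregnancy or non-diabetic medical reasons may be replaced in order to reach 23 subjects per study group to complete the study".

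Section 7.2 is the only text on allocation. Eligible patients are randomised to the three arms after consent, by the pharmacy, which keeps the code. Only the supplement and placebo arms are double blind. No exception is made for replacements, and replacements are not mentioned. The same section also says: "The investigator or pharmacy can deblind the subjects in the occurrence of any AE, SAE, or abnormality in a laboratory assessment", where the investigator thinks that the finding warrants permanent withdrawal.

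On who leaves and what follows: Section 10.3 states "Patients in the diet group have a risk of the occurrence of hypoglycemia during the study". Section 7.4.1 lists the withdrawal criteria, several of which rest on the investigator's opinion. Section 7.6 gives withdrawn patients no further trial follow-up. Section 9.1 analyses patients as randomised and names no method for a missing 3-month Microvascular Health Index (MHI).

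**The concern.** Three features of the rule work against each other or against the randomisation.

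- **Target.** The aim is a number of completers in each arm. Someone has to notice that a given arm is short and then add patients to that arm. Section 7.5 does not say who does this, or whether the new patient is randomised among three arms or placed in the short one.
- **Predictability.** The FMD arm is open. If recruiters know that the next place is an FMD place, they can choose, even without intent, whom to approach for a demanding diet. Allocation concealment exists to prevent this, and FMD v placebo is one of the two primary comparisons.
- **Reason.** Eligibility for replacement depends on why the patient left. Medical reasons count only if unrelated to diabetes, so diabetes-related withdrawals are left out by implication. In this population those are plausibly linked to treatment. For FMD patients the reason is classified by someone who knows the arm. For a capsule patient withdrawn over an adverse event, Section 7.2 may already have allowed unblinding.

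In addition, the exception to 90 has no upper limit.

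**Working it through.** **1. The target of 23.** Inputs from Section 4.4: difference 0.35, SD 0.41, two-sided alpha 0.05, two-sample t test. Exact power from the noncentral t distribution is 79.0% with 22 per arm and 80.8% with 23. So 23 is the smallest number that reaches 80%, and the plan's figure reproduces.

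**2. The allowance of 30.** 23 / (1 - 0.25) = 30.67, which rounds up to 31. With 30 per arm the expected number of completers is 30 x 0.75 = 22.5, just under the target.

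**3. How often an arm would be short.** An arm of 30 has fewer than 23 completers when it loses 8 or more. Let X be the number lost, X ~ Binomial(30, p), with drop-out independent between patients and arms (an assumption). Let q = P(X >= 8). The chance for at least one of three arms is 1 - (1 - q)^3.

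| Drop-out rate p | q, one arm | At least one of three arms |
|---|---|---|
| 20% | 0.239 | 0.56 |
| 25% (plan) | 0.486 | 0.86 |
| 30% | 0.719 | 0.98 |

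At 25%, all three arms reach 23 with probability (1 - 0.486)^3 = 0.136. Two or more arms are short with probability 3 x 0.486^2 x 0.514 + 0.486^3 = 0.48.

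These are chances of a shortfall. As chances that replacement is used because an arm can no longer reach 23, they are upper bounds: only listed reasons in the first 2.5 months qualify, replacement is optional, and the 25% in Section 7.5 also covers protocol violators. The 20% and 30% rows show the sensitivity to the rate.

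**4. Whether Section 7.2 can deliver the Section 7.5 target.** No ratio is stated. Three groups of 30 suggest equal allocation, which I assume. A newly randomised patient then enters a given short arm with probability 1/3, so on average 1 / (1/3) = 3 new patients are needed for each place in that arm. Ordinary randomisation therefore meets a per-arm target only by chance or by recruiting surplus patients into the other arms. Read together, the two sections leave either a target that cannot be relied on or placement in a named arm.

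**5. Where concealment is exposed.** For the capsule arms, the pharmacy holds the code and could assign supplement or placebo without telling site staff which. For the FMD arm that protection is absent.

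**6. What a shortfall costs in power.** The same exact t test against 23 placebo completers gives 79.9% with 22 FMD completers, 77.8% with 20 and 75.3% with 18. With 20 in both arms it is 74.9%. The loss is modest, so the replacement rule protects little.

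**7. Size of bias.** If k of 23 completers were selectively entered and their mean MHI change differed by s, the arm mean would move by (k/23) x s. The documents give neither k nor s, so I put no figure on it.

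**The case against.** The strongest reply is that nothing in the protocol departs from randomisation. Section 7.2 covers every eligible patient, places randomisation after consent and makes no exception. A reader might infer from 7.5 that replacements are put into a known arm instead of being randomised. The documents do not say so. What they contain is silence beside a target that ordinary randomisation cannot be relied on to meet.

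A reader might also infer that hypoglycaemia withdrawals are singled out. They are not named. Patient request, loss to follow-up and much noncompliance, all in Section 7.4.1, are not on the replaceable list either. Declining to backfill losses tied to the diet's own risk can also be defended.

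Nor does selective replacement by itself make the completers differ between arms. A patient who leaves is missing from the completers whether or not someone else is recruited. That imbalance comes from drop-out and from the absence of follow-up in Section 7.6. If replacements are properly randomised, the rule changes arm size and not composition.

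The pharmacy could track completers by arm without informing blinded staff, and 7.5 requires the reason for leaving to be evaluated and recorded. Finally, 90 is a planned number with a conditional exception. That is not a contradiction; what is missing is a cap.

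All of this stands. It narrows the point but leaves the central gap: the allocation route for replacements is unstated, the target is per arm, and one arm is open.

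**Conclusion.** The point holds as a gap in the allocation rule, not as a stated non-random procedure. Followed as written, 7.5 points towards filling a named arm. For the FMD arm such a place is foreseeable to recruiters, and concealment in FMD v placebo is weakened for those patients. The supplement v placebo comparison can be protected by the pharmacy. The reason-based condition adds discretion that, for FMD patients, is exercised with the arm known.

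The situation is likely to arise: at the plan's 25% drop-out the shortfall probabilities are 0.49 per arm and 0.86 for at least one arm. They rest on independent drop-out and are upper bounds on use of the rule. The documents support no estimate of bias, and the effect on power is small either way. The plan should be changed, since the remedy is wording and the exposed comparison is primary.

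**What to change.** In Section 7.5, drop the per-arm completer target and state that:

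- any additional patient is randomised after consent by taking the next unused number on the pharmacy's three-arm list, never a named arm, and the list is made long enough for this;
- additional recruitment is triggered by the pooled number of drop-outs, whatever the reason;
- a maximum total applies, and Sections 4.1 and 4.4 carry the same figure;
- replaced patients stay in the intention-to-treat population of the arm to which they were randomised. Section 9.1 already implies this, and 7.5 should confirm it.

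The cost is a protocol amendment and the loss of a guaranteed 23 per arm. Completer numbers may be unequal and some arms may end below 23: 20 v 23 completers gives 77.8% power, against 80.8% with 23 v 23. Simply deleting the replacement sentence is also possible, but at 25% drop-out it leaves at least one arm under 23 about 86% of the time.

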#### **7.6 Follow-up of subjects withdrawn from treatment**

No follow up will be done for subjects who are withdrawn from the study except for regularly follow up at the general practitioner. In case of withdrawal because of an adverse event, subjects are followed as described in paragraph 9.4.

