**Intervention:** One group receives a monthly 5-day fasting mimicking diet, one group receives daily 4 capsules of a food supplement and one group receives daily 4 placebo capsules, all for 3 consecutive months.

**Main study parameters:** The primary endpoint is an improvement of the Microvascular Health index in the diet group compared to the placebo group and in the food supplement group compared to the placebo group, after 3 months of the intervention.

Secondary endpoints: reduce albuminuria, decrease inflammation (urinary heparanase and MCP-1 expression, serum CRP and MCP-1 levels), reduce occurrence of specific urinary HS domains, improve metabolic parameters; fasting glucose, HbA1c, C-peptide, IGF-1, total cholesterol, LDL cholesterol, HDL cholesterol, and triglycerides serum levels, waist circumference, waist-to-hip ratio, body weight and systolic blood pressure after 3 months of the fasting mimicking diet and after 3 months of the food supplement.

The legacy effect of the interventions is also determined, 3 months after stopping with the intervention.

**Nature and extent of the burden and risks associated with participation, benefit and group relatedness:** Eligible patients are randomly assigned to the fasting mimicking diet, food supplement or placebo arm. At baseline, after 3 months and at 6 months, the MHI is measured by non-invasive SDF imaging of the microcirculation under the tongue, and blood and urine samples are collected. In the FMD arm, dosages of the hypoglycemic drugs are adapted during the 5 days of the diet prevent hypoglycemia. Glucose monitoring is done during the diet and at the end of each month in all intervention arms through a finger prick blood sample.

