### **6.5.3 Placebo**

The placebo capsule will mimic the Endocalyx capsules and will consist of microcrystalline cellulose and silicon dioxide.

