## 9. STATISTICAL ANALYSIS

### 9.1 Primary study parameter

SPSS will be used for all statistical analysis. Data analysis will be performed based on the intention to treat principle. Patients will be included in the analyses according to the treatment to which they were randomised.

The primary endpoint Microvascular Health index (MHI) will be summarized in mean with standard deviation or median with interquartile range. The effect within the group between baseline and 3 months is tested using a paired Student's t test (two-tailed). Differences in improvement of the MHI between baseline and 3 months between the FMD group and the placebo group and the food supplement and placebo group will be tested with an independent Student's t test.

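### Patients withdrawn before the 3-month visit get no further MHI measurement, so the primary t tests cannot cover the complete intention-to-treat population that sections 7.2 and 9.1 promise

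*Combined protocol and SAP*

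**What the plan says.** **Promise.** Section 9.1 adopts the intention-to-treat principle and states: "Patients will be included in the analyses according to the treatment to which they were randomised". Section 7.2 goes further: "Data will be presented for the complete intention-to-treat population as well as the per protocol population". The primary between-group test in 9.1 is an independent t test on the MHI change from baseline to 3 months, each active arm against placebo.

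**Measurement times.** The Summary says: "At baseline, after 3 months and at 6 months, the MHI is measured by non-invasive SDF imaging". Section 10.3 agrees: "Blood and urine sampling and non-invasive SDF imaging will be done at 3 time points in all intervention groups". There is no MHI between baseline and T4.

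**Withdrawal.** Section 7.4.1 lists criteria that require withdrawal from the trial. They include an adverse event or laboratory abnormality that the investigator judges to warrant it, and "patient noncompliance, defined as refusal or inability to adhere to the trial schedule or procedures". Section 7.4 adds 20% or more "weight loss or an allergic reaction to the food supplement or diet ingredients will be a reason for withdrawal from further participation".

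**After withdrawal.** Section 7.6 states: "No follow up will be done for subjects who are withdrawn from the study except for regularly follow up at the general practitioner". Its heading speaks of withdrawal from treatment, its text of withdrawal from the study. Its next sentence makes an exception for adverse-event withdrawals and refers to a paragraph 9.4. Section 9 ends at 9.3.

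**Missing data.** Sections 9.1 to 9.3 give no imputation, no model that handles missing outcomes, and no sensitivity analysis.

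**The concern.** A t test on change needs both values. Someone withdrawn before T4 has only the baseline MHI, so the test runs on patients with a T4 value, although the result would be reported as intention to treat.

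This matters if leaving is related to both arm and outcome. Some withdrawal reasons can depend on the intervention. Allergic reaction to a product ingredient, though probably rare, points to the active arms: "The placebo capsule will mimic the Endocalyx capsules and will consist of microcrystalline cellulose and silicon dioxide". The diet is unblinded and its burden differs from taking capsules, so unequal loss is most plausible for diet against placebo. It is less plausible for supplement against placebo, which is double-blind with the same capsule load. If patients who would have done worse leave one arm preferentially, that arm looks better than it is; the opposite pattern makes it look worse. A T4 value that was never collected cannot be recovered at the analysis stage.

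**Working it through.** **1. The plan's own figure.** Section 4.4 gives a difference of 0.35, SD 0.41, two-sided alpha 0.05, and 23 per group for 80% power. Exact noncentral-t power is 79.0% at 22 per group and 80.8% at 23, so 23 reproduces. With 30 enrolled and 25% loss, 30 × 0.75 = 22.5 remain, which is about 23.

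**2. Does any other text supply the missing value?**
- Section 7.4 says data generated up to discontinuation are analysed. Before T4 the only MHI is the baseline value.
- The 7.6 exception cites a paragraph that does not exist. Its apparent target, 8.4, follows the adverse event itself and does not provide for an MHI.
- Section 7.5 lets some drop-outs be replaced to reach 23 completers per group. That restores numbers, not the outcomes of those who left.
- Section 12.1(j) lets diet patients return to normal food without calling it withdrawal. Such patients still count if they attend T4, but this does not cover those withdrawn under 7.4 or 7.4.1.

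**3. Illustrative bias.** The documents give neither loss by arm nor the gap in MHI change between leavers and stayers, so both are assumed. With no true effect, and the gap in SD units (positive when leavers are worse):

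bias = 0.41 × (loss_FMD × gap_FMD − loss_placebo × gap_placebo)

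The type I error is the two-sided noncentral-t rejection rate at that bias.

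| Assumption | Bias | Measured per arm | Type I error |
|---|---|---|---|
| Equal loss, equal gap | 0 | any | 5.0% |
| 10% loss per arm, 0.5 SD gap in FMD only | 0.41 × 0.10 × 0.5 = 0.02 | 27, 27 | 5.4% |
| 25% loss per arm, 0.5 SD gap in FMD only | 0.41 × 0.25 × 0.5 = 0.05 | 23, 23 | 7.0% |
| Loss 35% FMD, 15% placebo, 0.5 SD gap in both | 0.41 × (0.175 − 0.075) = 0.04 | 20, 26 | 6.2% |
| 25% loss per arm, 0.85 SD gap in FMD only | 0.35 × 0.25 = 0.09 | 23, 23 | 10.9% |

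The 0.85 SD gap is 0.35/0.41, the gap that goes with leavers forgoing the whole planned gain. Reversing the assumptions reverses every sign.

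**4. What recovery buys.** Take 25% loss and a 0.5 SD gap in FMD only. Around the arm mean, stayers sit at +0.125 SD and leavers at −0.375 SD. If half of the leavers, typical of all leavers, have a T4 MHI, the bias is 0.41 × (0.75 × 0.125 − 0.125 × 0.375)/0.875 = 0.022. With 26 measured per arm, the type I error is 5.4%. Full recovery gives 0 and 5.0%.

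**5. What recovery costs in power.** SD is held at 0.41. If leavers gain nothing and all 30 per arm are measured:
- 10% loss: the difference is 0.35 × 0.90 = 0.315, power about 83%. The current plan measures 27 per arm at 0.35, about 87%.
- 25% loss: the difference is 0.35 × 0.75 = 0.2625, power about 68%. The current plan measures 23 per arm at 0.35, about 81%.
- 25% loss with half of the leavers recovered: 0.35 × 0.75/0.875 = 0.30 with 26 per arm, about 73%.

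If leavers at 25% loss are instead 0.5 SD worse, the difference is 0.35 − 0.25 × 0.5 × 0.41 = 0.299, and power with all 30 measured is about 79%. If they gain as much as completers, power is 90%.

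**The case against.** The strongest reply is that section 9.1 explains intention to treat as analysis by randomised arm, which the t tests can honour for everyone measured, and that the rest is labelling. This stands in part: renaming the analysis set and stating a missing-data rule would cure the label without new visits. It does not meet section 7.2, which promises the complete population, and it recovers no outcome.

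Three further limits stand:
- The adverse-event criterion is discretionary, so an investigator may keep such a patient in the study to T4. A reader might infer that any adverse event, or any lapse in taking the diet or capsules, ends measurement. The text does not say so: noncompliance is defined by the trial schedule and procedures.
- Known relevant food allergies are already excluded (4.3, 10.3), which limits allergy withdrawals. Laboratory withdrawals add little before T4, because blood is drawn only at T0, T4 and T5.
- Patients who withdraw consent, die or are lost cannot be measured under any wording.

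A reader might also infer that a quarter of each arm will lack a T4 MHI. Section 4.4 does call the 25% a drop-out rate, but 7.5 describes it as covering protocol violators as well, and a violator who attends T4 is not missing.

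**Conclusion.** The structural point holds with high confidence: as written, patients withdrawn before T4 leave the primary t tests, and nothing in the protocol replaces their outcome. The intention-to-treat label therefore claims more than the planned data collection supports, in both comparisons.

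The impact is not established. A reader might infer that the diet result will be biased in the diet's favour. The documents do not support that, since they give no loss rate by arm and nothing on how leavers would fare. The bias is zero if loss is unrelated to MHI change, or if loss rate times gap is the same in both arms. In the unequal cases shown, it is 0.02 to 0.09 on the MHI scale, 6% to 25% of the planned 0.35, with a type I error of 5.4% to 10.9%. All of these rest on assumed losses and gaps with SD 0.41. The recoverable group is mainly adverse-event, investigator-decided and partial-refusal withdrawals, and its size is not given. This should be fixed, because T4 values must be collected at the time and the visits are already scheduled.

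**What to change.** 1. In 7.4 to 7.6, separate stopping the intervention from leaving the study. Seek the scheduled T4 and T5 MHI in every randomised patient who has not withdrawn consent and can safely attend, including adverse-event withdrawals, and analyse it in the randomised arm. Medical reasons for stopping an intervention are unchanged.
2. Correct the reference to paragraph 9.4 in section 7.6.
3. Report missing T4 values by arm, with the reasons that 7.4 and 7.5 already require to be recorded.
4. In 9.1, add a delta-adjusted sensitivity analysis for T4 values still missing, with separate shifts per arm, for example −0.41 to +0.41. A 0.41 shift in one arm moves the difference by 0.10 × 0.41 = 0.04 at 10% missing and 0.25 × 0.41 = 0.10 at 25%; opposite shifts in the two arms double this. Imputation from baseline MHI alone does not remove bias when loss depends on the unobserved change.
5. If 7.6 is kept as written, describe the primary analysis as one of patients with a T4 MHI, not as complete intention to treat.

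**Cost.** A protocol amendment, one added analysis and some off-intervention visits. At 25% loss (7 to 8 per arm, 21 to 24 in total), two visits at 40 euros come to 21 × 2 × 40 = 1,680 to 24 × 2 × 40 = 1,920 euros. This lies within the 90 × 200 = 18,000 euros already implied by 10.5; staff cost is not given. Not all leavers will attend. The main downside is the possible dilution and loss of power shown in the last step of the working. No increase in enrolment is proposed.
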